4.1.4 Subject Enrollment and Randomisation

Study participation begins (ie, a subject is “enrolled”) once written informed consent is obtained. Once informed consent is obtained, a subject identification (SID) number will be assigned by a central system (eg, an interactive voice/web response system, [IXRS]) and the screening evaluations may begin to assess study eligibility (inclusion/exclusion) criteria. The SID number will be used to identify the subject during the screening process and throughout study participation, if applicable.

Approximately 40% of subjects (n = 16) enrolled in the study will have an eGFR of ≥ 30 and < 45 mL/min/1.73 m² and at least 40% (n = 16) will have an eGFR of ≥ 45 and < 60 mL/min/1.73 m². In addition, at least 50% of subjects (n=20) enrolled in the study should be taking insulin at a total daily dose of ≥ 20 units.

A master log of all consented subjects will be maintained at the site and will document all screening failures (ie, subjects who are consented but do not meet study eligibility criteria and/or are not randomised), including the reason(s) for screening failure.

Subjects who fail to meet the inclusion/exclusion criteria (ie, screening failures) should not, under any circumstances, be randomised or receive investigational product. There can be no exceptions to this rule. Subjects who are enrolled, but subsequently found not to meet all the eligibility criteria, should not be randomised or initiated on treatment. If randomisation and treatment initiation occur for a subject found not to meet any eligibility criterion, withdrawal of the subject from the study will be the decision of the medical monitor.

Subjects may be rescreened once if, in the opinion of the investigator, there is a reason to believe they may be eligible.

4.1.5 Withdrawal from the Study

Subjects are free to withdraw their consent to participate in the study (investigational product and assessments) at any time, without prejudice to further treatment. Subjects who withdraw consent will be asked about the reason(s) and the presence of any adverse events (AEs) and will be encouraged to remain in study for the remainder of the scheduled follow-ups. Adverse events will be followed up; diary cards and all study medications should be returned by the subject. If a subject withdraws from further participation in the study, then no further study visits or data collection should take place.

4.1.6 Discontinuation of Investigational Product

An individual subject will not receive any further investigational product if any of the following occur in the subject in question:

- 1 Withdrawal of consent from further treatment with investigational product
- 2 Lost to follow-up
- 3 An AE that, in the opinion of the investigator or the sponsor, warrants discontinuation of further dosing; specific examples include:
 - Dose-limiting symptoms with respect to GI tolerability and in particular if a subject requires intravenous fluids to treat volume depletion secondary to nausea and vomiting, even after measures are taken to reduce the risk of vomiting, after discussion with the medical monitor
 - $eGFR \leq 25 \text{ mL/min/1.73 m}^2$ on two consecutive blood tests
 - Acute kidney injury (AKI) in a subject as defined by:
 - An increase in serum creatinine by 0.3 mg/dL (26.5 $\mu\text{mol/L}$) within 48 hours in at least 2 readings
 - An increase in serum creatinine to 1.5 times baseline in at least 2 readings, which is known or presumed to have occurred within the prior 7 days
 - Subject noncompliance that, in the opinion of the investigator or sponsor, warrants withdrawal (eg, refusal to adhere to scheduled visits).
 - Pregnancy in a female subject
 - Subjects with persistent fasting glucose level of $> 260 \text{ mg/dL}$ (14.4 mmol/L) despite a MTD of rescue therapy to enable optimisation of the subject's glycaemic control
 - Any subject where Hy's Law criteria on liver function tests is met: AST or ALT $\geq 3 \times$ ULN **together with** Total bilirubin $\geq 2 \times$ ULN
 - Any subject who develops a life-threatening arrhythmia including sustained ventricular tachycardia, ventricular fibrillation or new ECG changes of second or third-degree heart block

Subjects who are permanently discontinued from receiving investigational product will be followed for protocol-specified assessments including follow-up of any AEs unless consent is withdrawn from further study participation (Section 4.1.5), the subject is lost to follow-up, the subject starts alternative treatment, or the subject is enrolled in another interventional clinical study.

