3.1.4 Management of Study Medication Related Toxicities and Dose Modification

Nausea and Vomiting

If a subject experiences nausea and vomiting in relation to investigational product, in the first instance, conservative measures should be advised including reducing meal size and maintaining adequate hydration. Where necessary, if there is persistent vomiting a subject may be given an antiemetic to control his/her symptoms; a 5HT3 receptor antagonist (eg, ondansetron) or cyclizine is preferable in this situation, rather than antiemetics which may affect gastric emptying, and in particular dopamine receptor antagonists (eg, metoclopramide or domperidone).

[REDACTED]

[REDACTED]

[REDACTED]	[REDACTED]	[REDACTED]
[REDACTED]	[REDACTED]	[REDACTED]
[REDACTED]	[REDACTED]	[REDACTED]

[REDACTED]

[REDACTED]	[REDACTED]	[REDACTED]
[REDACTED]	[REDACTED]	[REDACTED]
[REDACTED]	[REDACTED]	[REDACTED]

[REDACTED]

[REDACTED]

[REDACTED]	[REDACTED]	[REDACTED]	[REDACTED]
[REDACTED]	[REDACTED]	[REDACTED]	[REDACTED]
[REDACTED]	[REDACTED]	[REDACTED]	[REDACTED]
[REDACTED]	[REDACTED]	[REDACTED]	[REDACTED]

[REDACTED]

[REDACTED]

[REDACTED]

Management of Hyperglycaemia and Rescue Therapy

In subjects who have sustained hyperglycaemia [REDACTED] additional open-label rescue therapy should be considered by the investigator and should be documented in the relevant section of the CRF. For subjects where hyperglycaemia

is suspected, additional venous fasting plasma glucose measurements may be performed if necessary to investigate further.

Rescue therapy should be considered by the investigator following discussion with the medical monitor if any of the following apply:

- Fasting plasma glucose >200 mg/dL (11.1 mmol/L) on two occasions less than 8 days apart
- Three capillary plasma glucose levels > 250 mg/dL (13.9 mmol/L) in one week
- More than 30% of readings in hyperglycaemic range on CGM defined as > 250 mg/dL (13.9 mmol/L) in one week

If rescue medication is required, subjects should continue to participate in the study and receive their study medication. An interim prescription of the rescue medication will be provided by the study site if necessary, but continued prescription of rescue therapy will remain the responsibility of the primary care physician or usual diabetes physician. Rescue medication will not be provided by the Sponsor for this study.

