Investigators should consider discontinuing the investigational product in subjects with persistent fasting venous plasma glucose level of > 260 mg/dL (14.4 mmol/L), despite a maximum tolerated dose (MTD) of rescue therapy to enable optimization of the subject's glycaemic control. The subject should however remain in the study for all other study procedures and continued follow-up until their scheduled end of study date.

[Redacted]	[Redacted]
[Redacted]	[Redacted]
[Redacted]	[Redacted]
[Redacted]	[Redacted]
[Redacted]	[Redacted]
[Redacted]	[Redacted]

[REDACTED]

[REDACTED]

[REDACTED]

[REDACTED]

[REDACTED]

[REDACTED]

[REDACTED]

Management of Hypoglycaemia

A hypoglycaemic event is considered severe if associated with severe cognitive impairment requiring external assistance for recovery, as defined by the American Diabetes Association; clinically significant hypoglycaemia is defined as a capillary or venous plasma glucose reading of < 3.0 mmol/L (54 mg/dL). Spontaneous and clinically significant hypoglycaemia has not been experienced in prior studies with MEDI0382 up to a dose of [REDACTED] alongside metformin treatment.

All subjects will be provided with a diary and a glucose meter and will be advised to check their capillary plasma glucose level if they have symptoms of hypoglycaemia (hunger, dizziness, shaking, sweating, or irritability) or feel unwell and will be expected to record the level in their diary. Local protocols for treatment and follow-up of any hypoglycaemic episode should be followed. Any clinically significant hypoglycaemia should be reported by investigators as an AE regardless of whether or not the subject is experiencing symptoms or not. Pharmacological treatments administered for hypoglycaemia, eg, dextrose/glucose tablets, glucagon etc should be recorded in the electronic case report form (eCRF) as concomitant medications.

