For subjects who are found to have a decline in renal function to eGFR ≤ 25 mL/min/1.73 m² during the study, the subject should undergo a repeat eGFR level one week later, and if the eGFR remains ≤ 25 mL/min/1.73 m² on a second consecutive test, the investigational product (IP) should be discontinued, and the subject should also be advised to stop metformin therapy (if they have not already done so) and any other medications that are contraindicated for this degree of renal impairment. However, the subject should remain in the study for all other study procedures until their scheduled end of study.

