5.4.1 Time Period for Collection of Adverse Events

AEs will be collected from time of signature of informed consent, throughout the treatment period, and including the follow-up period (Day 60±5).

All SAEs will be recorded from the time of informed consent.

For nontreatment-emergent AEs (ie, AEs that occur during the period from the time informed consent is signed but prior to the subject receiving investigational product), only AEs associated with protocol-related procedures should be reported. After the start of treatment, all treatment-emergent AEs (TEAEs; Section 5.1) should be reported.

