5.4.2 Follow-up of Unresolved Adverse Events

Any AEs that are unresolved at the subject's last AE assessment in the study are followed up by the investigator for as long as medically indicated, but without further recording in the eCRF. MedImmune retains the right to request additional information for any subject with ongoing AE(s)/SAE(s) at the end of the study, if judged necessary.

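### Protocol Section 4.1.6 ends follow-up when a subject off product starts alternative treatment, which conflicts with Section 3.1.4 and can cost the Day 32 MMTT

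*Protocol*

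**What the plan says.** Section 4.1.6 of the protocol closes with a follow-up rule: "Subjects who are permanently discontinued from receiving investigational product will be followed for protocol-specified assessments including follow-up of any AEs unless consent is withdrawn". The remaining exits are that "the subject is lost to follow-up, the subject starts alternative treatment, or the subject is enrolled in another interventional clinical study". No section defines alternative treatment.

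Section 3.1.4 deals with three related situations.

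- **Rescue while still on product.** "If rescue medication is required, subjects should continue to participate in the study and receive their study medication".
- **Product stopped for persistent fasting glucose above 260 mg/dL despite rescue at its highest tolerated dose.** The stated purpose is better glycaemic control. "The subject should however remain in the study for all other study procedures and continued follow-up until their scheduled end of study date".
- **Product stopped for eGFR of 25 or below on two consecutive tests.** Here "the subject should also be advised to stop metformin therapy (if they have not already done so) and any other medications that are contraindicated" at that level of renal function. "However, the subject should remain in the study for all other study procedures until their scheduled end of study".

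Section 6.3 counts a subject as a completer if followed to the last visit or assessed for the primary endpoint, whatever number of doses was taken. It names only withdrawn consent and loss to follow-up as non-completion.

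In the SAP, Section 3.4.1.2 leaves out of the primary analysis anyone without a valid baseline or Day 32 MMTT. Section 3.1 imputes nothing outside the AUC calculation. Section 3.4.2.2 applies the same exclusion to HbA1c, fasting glucose and CGM time in range; only weight is carried forward.

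**The concern.** The subject stopped for hyperglycaemia is the one most likely to be given a different glucose-lowering drug. Section 3.1.4 tells the site to keep that subject. Section 4.1.6, read literally, tells the site to stop assessments once the new drug begins. Nothing visible says which section prevails, so two sites could handle the same subject differently.

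The day on which the new drug starts decides what is lost. Before Day 32, the primary endpoint goes, along with the Day 32 secondary glycaemic endpoints. The reason for the loss is poor glucose control or poor tolerability, so the subjects left out differ systematically from those kept, in an analysis labelled intent-to-treat. After Day 32, the loss is confined to follow-up data, mainly safety.

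**Working it through.** **1. The plan's own figure.** Protocol 4.8.2 and SAP 2.4 give a difference of 18.1, SD 20, 20 completers per arm and two-sided alpha 0.10. The standardised difference is 18.1 / (20 × √(1/20 + 1/20)) = 18.1 / 6.325 = 2.862. Normal power is Φ(2.862 − 1.645) = Φ(1.217) = 88.8%; exact t power is 87.8%. Both agree with the stated figure of more than 85%, which this point does not challenge.

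**2. The retention rules side by side.**

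| Reason for stopping product | Retention rule in 3.1.4 | Effect of the 4.1.6 exit |
|---|---|---|
| Persistent fasting glucose > 260 mg/dL | Stay to scheduled end | Direct conflict once a new treatment starts |
| eGFR ≤ 25 on two tests | Stay to scheduled end | Conflict only if a substitute drug is started |
| GI intolerance, AKI, Hy's Law, arrhythmia | None visible | 4.1.6 is the operative rule |
| Rescue while on product | Stay, on product | Exit does not apply |

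**3. What one affected subject loses.** Tables 10 and 11 schedule V8 on Day 19, V9 on Day 32, V10 on Day 33, V11 on Day 40 and V12 on Day 60. Assume that the new treatment starts on the day of the stop, and count AE collection to Day 60.

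- Day 12: V8 to V12, 5 visits; 60 − 12 = 48 days.
- Day 19: V9 to V12, 4 visits; 60 − 19 = 41 days.
- Between Day 19 and Day 31: the same 4 visits; 41 days falling to 60 − 31 = 29.
- New treatment on Day 33, MMTT already done: V11 and V12, 2 visits; 60 − 33 = 27 days.

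The first three cases lose the only post-baseline MMTT. The Day 12 case fits an eGFR of 25 or below on Day 5 that is confirmed a week later, but only if a substitute is then started.

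**4. Power if Day 32 tests are lost and not replaced (counts assumed).** Exact t power is 87.0% for 20 against 19, 86.2% for 20 against 18, 85.2% for 20 against 17 and 84.1% for 20 against 16. Power is a minor issue here.

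**5. How selection would carry through (illustration, not an estimate).** If k of 20 subjects in an arm are left out and their AUC change would have been D points worse than the rest, the analysed arm mean is too favourable by kD/20. For k = 1 and D = 10 that is 0.5 points; for k = 3 and D = 30 it is 4.5 points, against a design difference of 18.1. Losses on placebo would shrink the apparent effect; losses on active would inflate it. The documents give neither k nor D.

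**The case against.** The best reply is that Section 3.1.4 is the more specific text, that Section 6.3 does not list alternative treatment among the reasons for non-completion, and that a careful site would therefore keep the subject. Affected subjects may be few: persistent glucose above 260 mg/dL despite full rescue is unlikely early in a 32-day treatment period. This lowers the likely impact but leaves the conflict in place, because no visible text ranks the sections and 3.1.4 shows no retention rule for the other stoppers. Parts of 3.1.4 are redacted, so the absence of an exception or a further rule there cannot be fully confirmed.

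Four stronger readings are tempting and are not supported.

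- **That 4.1.6 contradicts Section 5.4.1.** That section says "AEs will be collected from time of signature of informed consent, throughout the treatment period, and including the follow-up period". It sets a general window, and it makes no exception for withdrawn consent or loss to follow-up either. A stated exit from a general window is not a contradiction.
- **That every eGFR stopper falls under the exit.** Section 3.1.4 tells that subject to stop drugs and does not mention starting one.
- **That the SAP treats an off-product Day 32 MMTT as invalid.** Table 10 asks for the 2.5-hour interval after dosing only where relevant, Section 6.3 disregards the number of doses, and SAP 3.1 uses all available data. These point towards using the test, although SAP 3.4.1.2 does not say so.
- **That safety data are left unprotected.** Deaths (5.4.3), possible Hy's Law cases (10.5.3) and pregnancies (5.6.3.1) have their own rules, and unresolved events are "followed up by the investigator for as long as medically indicated, but without further recording in the eCRF". What remains exposed is the recording of ordinary events that continue or begin after the exit.

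Replacement under 4.1.7, limited to three subjects who withdraw, could restore numbers but not the missing outcomes.

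**Conclusion.** The alternative-treatment exit in 4.1.6 conflicts with the 3.1.4 rule for the subject stopped for hyperglycaemia and fits poorly with Section 6.3. It would conflict with the eGFR rule too if a substitute drug were started, and for the remaining stoppers nothing visible overrides it. Loss of the primary endpoint requires three things: product is permanently stopped, new treatment begins before Day 32, and the site follows 4.1.6 as written. SAP 3.4.1.2 then excludes the subject for a reason related to outcome.

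Per subject the loss is 4 or 5 visits and 29 to 48 days of AE collection for stops from Day 12 to Day 31, assuming that treatment starts on the day of the stop; it is smaller if treatment starts later. A reader might infer that the trial result is biased or underpowered. The documents do not support that, because the number of such subjects is unknown and the stated power holds.

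**What to change.** In the last paragraph of protocol Section 4.1.6, delete the alternative-treatment exit and add, for example: *Subjects who stop investigational product and start other glucose-lowering treatment stay in the study for every scheduled visit, including the Day 32 MMTT and AE collection to Day 60.*

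As an optional clarification, confirm in SAP 3.4.1.2 that a Day 32 MMTT taken off product is used in the ITT analysis, and add a sensitivity analysis that excludes MMTTs taken after a new treatment was started. How values after a switch enter the primary analysis is partly a choice of estimand, so the sponsor should make it explicitly.

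The cost is one protocol sentence and one or two SAP sentences. The visits are already scheduled, so the added work is carrying them out for stopped subjects. The drawback is that some Day 32 values will partly reflect the new treatment. This could move the difference either way: an effective new drug in a placebo stopper would narrow it, a placebo stopper who stays poorly controlled could widen it, and active-arm stoppers can act in either direction. The sensitivity analysis would show how much this matters.

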4.1.7 Replacement of Subjects

Subjects who withdraw from the study will be replaced where possible. A maximum number of three subjects may be replaced during the study.

4.1.8 Withdrawal of Informed Consent for Data and Biological Samples

Biological Samples Obtained for the Main Study

Study data are protected by the use of an SID number, which is a number specific to the subject. The investigator is in control of the information that is needed to connect a study sample to a subject. A subject's consent to the use of data does not have a specific expiration date, but the subject may withdraw consent at any time by notifying the investigator. If consent is withdrawn, any samples collected prior to that time may still be given to and used by the sponsor but no new data or samples will be collected unless specifically required to monitor safety of the subject.

[REDACTED]

[REDACTED]

[REDACTED]

[REDACTED]

4.2 Schedule of Study Procedures

Whenever vital signs, 12-lead ECGs, and blood draws are scheduled for the same nominal time, blood draws should occur last. The timing of the first two assessments should be such that it allows the blood draw (eg, PK blood sample) to occur at the proper nominal time.

4.2.1 Enrollment/Screening Period

Table 9 shows all procedures to be conducted at the screening visit and run-in procedures.

Table 9 Screening and Run-in Procedures

Study Period	Screening	Run-in		
Visit Number	V1	V2	V3 ^a	Remote contact
Procedure / Study Day	D-40 to D-15	D-14	D-5	D-1
Written informed consent/ assignment of SID number	X			
[REDACTED]	■			
[REDACTED]	■			
[REDACTED]	■			
Outpatient visit to clinic ^c	X	X	X	
Medical history	X			
Physical examination (full)	X			
Weight, height and BMI calculation	X			
ECG	X			
Vital signs ^{d, e}	X		X ^e	
Collect blood for				
Serum chemistry (including eGFR calculation)			X	
LFTs, Cr, and eGFR calculation	X			
Haematology (FBC)	X		X	
HbA1c	X			
Calcitonin	X			
HIV-1 and -2 antibodies; hepatitis B and C serology	X			

AEs = adverse events; ABPM = ambulatory blood pressure monitoring; BMI = body mass index; BP = blood pressure; CGM = continuous glucose monitoring; CR = creatinine; D = Day; ECG = electrocardiogram; eGFR = estimated glomerular filtration rate; FBC = full blood count; GLP-1 = glucagon-like peptide-1; HbA1c = glycated haemoglobin; HIV = human immunodeficiency virus; IFU = instructions for use; LFT = liver function tests (albumin; alanine transaminase [ALT], aspartate transaminase [AST], alkaline phosphatase [ALP], and total bilirubin); MMTT = mixed meal tolerance test; PK = pharmacokinetic; SAE = serious adverse events; SC = subcutaneous; SID = subject identification; V = visit

- a Subjects are required to fast for at least 8 hours overnight prior to the visit. Subjects are permitted to drink water during this period of fasting. For days where subjects are required to fast the investigator/study team may need to consider dose [REDACTED]
- b [REDACTED]
- c The diet of subjects should not be restricted in any way during the study (unless fasting or a standardised liquid meal is specified).
- d Blood pressure should be measured at heart level and opposite to the arm where the CGM device is applied, with the subject supine and rested for 10 minutes prior to the measurement. * Day-5: vital signs to be taken prior to fitting the ABPM device
- e Vital Signs Schedule (blood pressures, pulse rate, respiratory rate, and temperature): on days where ABPM is due to be checked a set of vital signs should be performed prior to application of the ABPM cuff. Blood pressure should be measured at heart level and opposite to the arm where the CGM device is applied, with the subject supine and rested for 10 minutes prior to the measurement. For time points where ECG recording precedes vital sign measurement, the 10-minute rest in the supine position prior to the ECG suffices for the rest prior to vital sign measurement.
- f Following a minimum 8-hour fast overnight, a blood sample for glucose will be taken immediately (within 15 minutes) prior to the subject drinking one entire can of Ensure Plus as a standardised meal (ie, '0 minutes'). Blood samples for glucose will additionally be drawn at 15, 30, 45, 60, 90, 120, 180 and 240 minutes (\pm 5 minutes) after consumption of the standardised meal.
- g Urine sample for urine albumin/creatinine ratio at Visit 1 screening may be taken at any time and does not need to be a first void specimen. At Visit 2 (Day-14) and Visit 3 (Day -5) urine sample for urine albumin / creatinine ratio should be taken as an early morning specimen during the first void of the day.
- h Pregnancy tests do not need to be conducted in women who are surgically sterile (ie, bilateral tubal ligation, bilateral oophorectomy, or complete hysterectomy) or are post-menopausal (defined as at least 1 year since last menses and/or having an elevated follicle stimulating hormone laboratory value which is in the post-menopausal range in previous laboratory test results).
- i CGM device should be worn continuously throughout the study until V11 and the sensor should be applied to the arm, taking into account subject preference and which side the ABPM device will be used. The sensor applied to the skin is single use and may not be re-attached once removed.
- j Subjects will be fitted with the ABPM device whilst at the clinical unit, which may involve practice inflations. The ABPM device should be applied on the arm contralateral to the arm where the CGM device is applied. The subject will then wear the monitor / cuff for approximately 24 hours and will remove at the end of the 24-hour period whilst at home and will return the monitor at their next visit.
- k [REDACTED]
- l Subject's ability to self-administer investigational product will be verified using normal saline subcutaneous injections as required by the subjects until they feel confident in self-injection. Training will be given to familiarise subject with Instructions for Use (IFU) booklet and to assess suitability for self-injection using the prefilled syringe (PFS).
- m [REDACTED]

- ° A glucose meter, test strips and diary should be provided to the subject. The subject should be trained in its use and advised to test their capillary plasma glucose at any time the subject feels unwell or has symptoms of hypoglycaemia (hunger, dizziness, shaking, sweating or irritability).

